ILAE	International League Against Epilepsy
IMP	investigational medicinal product
IND	Investigational New Drug

IRB	Institutional Review Board
IRT	interactive response technology
IVRS	interactive voice response system
IWRX	interactive web response system
LEV	levetiracetam
MedDRA	Medical Dictionary for Regulatory Activities
MRI	magnetic resonance imaging
NDA	New Drug Application
PDILI	potential drug-induced liver injury
PK	pharmacokinetic(s)
PK-PPS	Pharmacokinetic Per-Protocol Set
PMDA	Pharmaceuticals and Medical Devices Agency
PPS	Per-Protocol Set
PS	Patient Safety
RBC	red blood cell
SAE	serious adverse event
SAP	Statistical Analysis Plan
SOP	Standard Operating Procedure
SPC	Summary of Product Characteristics
SS	Safety Set
TEAE	treatment-emergent adverse event
TMF	trial master file
ULN	upper limit of normal
VNS	vagal nerve stimulation
WBC	white blood cell

This document cannot be used to support any marketing authorization application and any extensions or variations thereof.

1 SUMMARY

EP0100 is an open-label, single-arm, multicenter study with levetiracetam (LEV) as monotherapy or adjunctive treatment to evaluate the efficacy and safety of LEV in Japanese subjects aged 1 month to <4 years with partial seizures. The study will consist of 2 periods. The First Period is designed to confirm efficacy of LEV, and the Second Period is designed to evaluate the long-term efficacy and safety of LEV. Subjects with uncontrolled partial seizures will be enrolled into the Selection Period of the First Period.

Seizure counts during the 2 weeks prior to Visit 1 will be used as a Retrospective Baseline. All eligible subjects will enter a 6-week Evaluation Period. Subjects aged 1 month to <6 months will be started on LEV 14mg/kg/day at Visit 3 (Week 0). The dose may be increased by LEV 14mg/kg/day for subjects aged 1 month to <6 months at 2-week intervals to a maximum dose of 42mg/kg/day. Subjects aged 6 months to <4 years will be started on LEV 20mg/kg/day at Visit 3 (Week 0). The dose may be increased by LEV 20mg/kg/day at 2-week intervals to a maximum dose of 60mg/kg/day.

At Visit 6 (Week 6), subjects may enter the Second Period or enter the Down-Titration Period followed by a Safety Follow-Up Period. Subjects who do not enter the Second Period will be down-titrated. The dose will be decreased by LEV 14mg/kg/day for subjects aged 1 month to <6 months or by LEV 20mg/kg/day for subjects aged 6 months to <4 years at 2-week intervals to 0mg/kg/day. Subjects who withdraw from the study at the minimum age-related dose do not need to down-titrate. In order to provide LEV to subjects who completed the First Period, the Second Period will be conducted until approval or the program is discontinued.

All subjects who do not enter the Second Period will enter the Safety Follow-Up Period, regardless of whether they down-titrate LEV.

After approval in Japan for the indication of LEV as monotherapy or adjunctive treatment in patients aged 1 month to <4 years with partial seizures, this clinical study (Phase 3) will be continued as a postmarketing clinical study (Phase 4). All subjects who are still in the study as of the date of approval will be considered to have completed the study. After the date of approval, subjects should visit the investigational site as soon as possible to complete the study by switching to commercial LEV or discontinuing LEV after the assessments specified in Section 8.5 "Early Discontinuation Visit" in the protocol.

After the study is continued as a postmarketing clinical study (Phase 4), the LEV dry syrup 50% prescribed during the study period will continue to be used, and the labeling of the IMP will not be changed. There will also be no change in the handling and storage conditions of the IMP.

After the date of approval, EP0100 shall be continued as a postmarketing clinical study (Phase 4), and the description of EP0100 in this protocol shall read as follows. The term "clinical study" should be replaced with "postmarketing clinical study," the term "clinical trial" should be replaced with "postmarketing clinical study", the term "this (clinical) study" should be replaced with "this postmarketing clinical study", the term "protocol" should be replaced with "postmarketing clinical study protocol", the term "investigator" should be replaced with "investigator for postmarketing clinical study", the term "subinvestigator" should be replaced with "subinvestigator for postmarketing clinical study", the term "IMP" should be replaced with "IMP for postmarketing clinical study ", the term "Investigator's Brochure" should be replaced with "package insert or precautions information", the term "Phase 3" should be replaced with

"Phase 4", the term "subject's ID card" should be replaced with "subject's ID card for postmarketing clinical study participation", and the term "Good Clinical Practice (GCP)" should be replaced with "GCP and Good Postmarketing Study Practice (GPSP)".

2 INTRODUCTION

Epilepsy is one of the most common and challenging neurological disorders. About 65 million people worldwide are estimated to have epilepsy (Thurman et al, 2011). In Japan, the number of patients with epilepsy is estimated to be approximately 216,000 (MHLW, 2011). In addition, epilepsy affects 0.5% to 1% of the Japanese population (Inoue, 2005). There is also a report that suggests the total number of patients with epilepsy in Japan is approximately 1 million (Ueda, 2007). The incidence varies greatly with age, with high rates occurring in childhood, falling to low levels in early adult life, but with a second peak in those aged over 65 years. In many people, particularly children, the condition may remit, although a significant proportion will have epilepsy lifelong. The disease duration is often determined by the underlying cause. As appropriate treatment in the initial stages of epilepsy is said to have a major impact on prognosis and mental development (Berg et al, 2014; Kwan and Brodie, 2001), it is important to provide appropriate pharmacotherapy at an early stage and prescribe treatment with a high level of safety in order to maintain patients' daily and social activities in their long lives ahead.

Levetiracetam has been developed as adjunctive therapy in the treatment of partial seizures in children aged 1 month to <4 years with epilepsy in N01009 and the open-label extension study N01148. The European Medicines Agency (EMA) and US Food and Drug Administration (FDA) approved the indication of adjunctive treatment in children down to 1 month of age with partial seizures in Sep 2009 and Dec 2011, respectively, UCB also conducted a noninterventional, post authorization safety study (N01357, Jan 2011 through Nov 2013), as agreed with the EMA. The objective of the study was to collect safety and efficacy data on Keppra® in clinical practice in subjects aged 1 month to <12 months with epilepsy. The study was conducted as a part of a risk management plan after obtaining approval for the indication in the EU (Sep 2009).

In Japan, an open-label, single-arm, multicenter study (N01223) demonstrated that long-term adjunctive treatment with LEV (20mg/kg/day or 1000mg/day to 60mg/kg/day or 3000mg/day) was effective in Japanese children aged 4 to <16 years with partial seizures. The Pharmaceuticals and Medical Devices Agency (PMDA) approved the indication of LEV as adjunctive therapy in Japanese children aged 4 to <16 years with uncontrolled partial seizures in May 2013.

For the purpose of this study, the seizure type classification will follow the 1981 International League Against Epilepsy (ILAE) classification of epileptic seizures, which speaks of partial seizures, classified as simple partial seizures (no alteration of consciousness), complex partial seizures (with alteration of consciousness), and secondarily generalized seizures, and defines generalized seizure types, referred to as absence seizures (typical and atypical), myoclonic seizures, clonic seizures, tonic seizures, tonic-clonic seizures, and atonic seizures. Apart from myoclonic seizures, consciousness is almost invariably impaired from the onset of the seizure (ILAE, 1981, Appendix 1 [Section 17.1]).

Likewise, the classification of epilepsy syndromes will be used according to the 1989 ILAE-publication (ILAE, 1989, Appendix 2 [Section 17.2]).

This study is designed to confirm the dosage and administration for Japanese subjects aged 1 month to <4 years. The First Period is designed to confirm efficacy of LEV, and the Second Period is designed to evaluate the long-term efficacy and safety of LEV.

EP0100 was initially started with a design to evaluate the efficacy of LEV using the percent reduction from Baseline in partial seizure frequency based on the number of seizures recorded by video-electroencephalography (EEG) as the primary efficacy endpoint, but subject recruitment was extremely difficult. One of the major factors for the difficulty in recruitment was that the 48h video-EEG measurement was to be performed 3 times at Baseline, Week 2, and Week 6, thus increasing the burden on the subject/guardian. As a result, consent to participate in the study was not obtained from the guardian, and many potential subjects could not be screened for entry into the study. After consultation with the PMDA, the method of recording seizures was changed to a conventional patient diary, and the primary endpoint was changed to percent reduction in partial seizure frequency based on the patient diary. The percent reduction in partial seizure frequency calculated from the 48h video-EEG is included as an “other” efficacy variable.

3 STUDY OBJECTIVES

3.1 Primary objective

The primary objective of this study is to confirm the efficacy of LEV in reducing seizure frequency in the First Period compared to historical control as adjunctive treatment in pediatric epilepsy subjects aged 1 month to <4 years with partial seizures.

3.2 Secondary objectives

The secondary objectives are the following:

- To evaluate the safety and tolerability of LEV in the First Period in pediatric epilepsy subjects aged 1 month to <4 years with partial seizures
- To evaluate the efficacy of LEV in reducing seizure frequency in the First Period compared to historical control as monotherapy in pediatric epilepsy subjects aged 1 month to <4 years with partial seizures
- To evaluate long-term safety and tolerability of LEV in the combined First and Second Periods in pediatric epilepsy subjects aged 1 month to <4 years with partial seizures receiving long-term treatment with LEV at individualized doses
- To evaluate the efficacy of LEV in the combined First and Second Periods as monotherapy or adjunctive treatment in pediatric epilepsy subjects aged 1 month to <4 years with partial seizures
- To characterize pharmacokinetics (PK) of LEV in the First and Second Periods in epileptic pediatric subjects aged 1 month to <4 years

4 STUDY VARIABLES

4.1 Efficacy variables

Efficacy variables are defined separately for the First Period and the combined First and Second Periods, and for the type of therapy, if applicable.

4.1.1 Efficacy variables for subjects on adjunctive therapy

4.1.1.1 Primary efficacy variable

4.1.1.1.1 First Period

The primary efficacy variable for subjects on adjunctive therapy is the percent reduction in partial seizure frequency per week from Baseline to Visit 6.

4.1.1.1.2 Combined First and Second Periods

There is no primary efficacy variable for the combined First and Second Periods for subjects on adjunctive therapy.

4.1.1.2 Secondary efficacy variables

4.1.1.2.1 First Period

The secondary efficacy variable for the First Period is the following:

- Percent reduction in partial seizure frequency per week from Baseline to Visit 4 and Visit 5

4.1.1.2.2 Combined First and Second Periods

The secondary efficacy variables for the combined First and Second Periods are the following:

- For each visit, percent reduction in partial seizure frequency per week from Baseline
- For each visit, percent reduction in partial seizure frequency per week from Baseline grouped into 6 categories: <0%, 0% to <25%, 25% to <50%, ≥50%, ≥75%, and 100%

4.1.1.3 Other efficacy variables

4.1.1.3.1 First Period

The other efficacy variables for the First Period for the number of seizures based on the 48h video-EEG recorded through Protocol Amendment 2 are the following:

- Percent reduction in average daily frequency (ADF) of partial seizure frequency monitored by the 48h video-EEG at Visit 4 and Visit 6 compared to Baseline
- Percent reduction in ADF of partial of seizure frequency monitored by the 48h video-EEG grouped into 6 categories: <0%, 0% to <25%, 25% to <50%, ≥50%, ≥75%, and 100% based on the Evaluation Period 48h video-EEG at Visit 4 and Visit 6 compared to Baseline

4.1.1.3.2 Combined First and Second Periods

The other efficacy variables for the combined First and Second Periods are the following:

- For each visit, percent reduction in all type of seizure frequency per week from Baseline
- For each visit, percent reduction in all type of seizure frequency per week from Baseline grouped into 6 categories: <0%, 0% to <25%, 25% to <50%, ≥50%, ≥75%, and 100%

4.1.2 Efficacy variables for subjects on monotherapy

4.1.2.1 Primary efficacy variable for subjects on monotherapy

There is no primary efficacy variable for subjects on monotherapy.

4.1.2.2 Secondary efficacy variables

4.1.2.2.1 First Period

There is no secondary efficacy variable for the First Period.

4.1.2.2.2 Combined First and Second Periods

The secondary efficacy variables for the combined First and Second Periods are the following:

- For each visit, percent reduction in partial seizure frequency per week from Baseline
- For each visit, percent reduction in partial seizure frequency per week monitored by the patient diary from Baseline grouped into 6 categories: <0%, 0% to <25%, 25% to <50%, $\geq 50\%$, $\geq 75\%$, and 100%

4.1.2.3 Other efficacy variables

4.1.2.3.1 First Period

The other efficacy variables for the First Period for the number of seizures based on the 48h video-EEG recorded through Protocol Amendment 2 are the following:

- Percent reduction in ADF of partial seizure frequency monitored by the 48h video-EEG to Visit 4 and Visit 6 compared to Baseline
- Percent reduction in ADF of partial of seizure frequency monitored by the 48h video-EEG grouped into 6 categories: <0%, 0% to <25%, 25% to <50%, $\geq 50\%$, $\geq 75\%$, and 100% based on the Evaluation Period 48h video-EEG at Visit 4 and Visit 6 compared to Baseline

4.1.2.3.2 Combined First and Second Periods

The other efficacy variables for the combined First and Second Periods are the following:

- For each visit, percent reduction in all types of seizure frequency per week from Baseline
- For each visit, percent reduction in all types of seizure frequency per week from Baseline grouped into 6 categories: <0%, 0% to <25%, 25% to <50%, $\geq 50\%$, $\geq 75\%$, and 100%
- Percentage of subjects who are continuously 6-month seizure-free monitored by the patient diary

4.2 Pharmacokinetic and pharmacodynamic variables

Levetiracetam (parent compound only) plasma levels is defined as the other PK variable.

4.3 Safety variables

4.3.1 Primary safety variable

There is no primary safety variable.

4.3.2 Secondary safety variables

4.3.2.1 First Period

The secondary safety variables for the First Period are the following:

- Incidence of treatment-emergent adverse events (TEAEs)
- Incidence of treatment-emergent serious adverse events (SAEs)
- Incidence of TEAEs leading to discontinuation from study medication

4.3.2.2 Combined First and Second Periods

The secondary safety variables for the combined First and Second Periods are the following:

- Incidence of TEAEs
- Incidence of treatment-emergent SAEs
- Incidence of TEAEs leading to discontinuation from study medication

4.3.3 Other safety variables

The other safety variables are the following:

- Adverse events (AEs) (variables other than secondary safety variables)
- Laboratory tests (blood chemistry and hematology)
- Vital signs
- Body weight and height
- Physical and neurological examination

5 STUDY DESIGN

5.1 Study description

5.1.1 Overall

EP0100 is an open-label, single-arm, multicenter study with LEV as monotherapy or adjunctive treatment to evaluate the efficacy and safety of LEV (14mg/kg/day to 42mg/kg/day for subjects aged at 1 month to <6 months, 20mg/kg/day to 60mg/kg/day for subjects aged at 6 months to <4 years) in the treatment of partial seizures over the First Period (6 weeks), followed by the long-term follow-up (Second Period) in pediatric subjects.

5.1.2 First Period

Eligible subjects will enter the First Period (6 weeks). Subjects aged 1 month to <6 months will be started on LEV 14mg/kg/day at Visit 3 (Week 0). The dose may be increased by LEV 14mg/kg/day for subjects aged 1 month to <6 months at 2-week intervals to a maximum dose of LEV 42mg/kg/day. Subjects aged 6 months to <4 years will be started on LEV 20mg/kg/day at Visit 3 (Week 0). The dose may be increased by LEV 20mg/kg/day at 2-week intervals to a maximum dose of 60mg/kg/day. The dose will be increased if seizure freedom has not been

attained according to the patient diary. However, if there is a safety concern for the subject in the opinion of the investigator, the dose can be kept.

For the subjects aged 1 month to <12 months who have cluster seizures several times a day and are being treated on an inpatient basis under a physician's supervision, the dose can be increased without waiting for the 2-week interval. If the subject is hospitalized and under supervision of a physician, the following rapid titration procedure (dose and interval) will be performed as the most rapid case: dose increments of LEV 14mg/kg/day for subjects aged 1 to <6 months and LEV 20mg/kg/day for subjects aged 6 months to <4 years at 1-day intervals.

If an intolerable AE occurs during the First Period, the dose can be decreased only once as a fallback option. The dose will be decreased by LEV 14 mg/kg/day for subjects aged 1 month to <6 months or LEV 20mg/kg/day for subjects aged 6 months to <4 years. After decreasing the dose, a re-increase will not be allowed during the First Period.

At Visit 6 (Week 6), subjects may enter either the Second Period or the Down-Titration Period, followed by the Safety Follow-Up Period. Subjects who do not enter the Second Period will be down-titrated. The dose will be decreased by LEV 14mg/kg/day for subjects aged 1 month to <6 months or by LEV 20mg/kg/day at 2-week intervals to 0mg/kg/day. Subjects who withdraw from the study at the minimum age-related dose do not need to down-titrate.

All subjects who do not enter the Second Period will enter the Down-Titration Period, followed by the Safety Follow-Up Period.

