5.1.5 Planned number of subjects and sites

The planned number of evaluable subjects in the First Period will be a total of 38 subjects for the primary efficacy analysis. Subjects will be enrolled into 4 age groups (1 month to <6 months, 6 months to <1 year, 1 year to <2 years, and 2 years to <4 years), with a minimum of 5 subjects in each age group.

The planned number of monotherapy subjects will be a total of 10 subjects.

It is planned to have those subjects recruited in approximately 20 sites.

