6.1 Inclusion criteria

To be eligible to participate in this study, all of the following criteria must be met:

- 1a. An Institutional Review Board (IRB)/Independent Ethics Committee (IEC) approved written Informed Consent form is signed and dated by the parent(s) or legal representative. Subject/legal representative/caregiver is considered reliable and capable of adhering to the protocol (eg, able to understand and complete diaries), visit schedule, or medication intake according to the judgment of the Investigator.
- 2a. Subject must have a diagnosis of epilepsy with partial onset seizures (ie, seizures of focal onset), whether or not secondarily generalized.
Subject has had an EEG and a brain computerized tomography (CT) scan or brain magnetic imaging (MRI) consistent with a diagnosis of localized epilepsy according to the International Classification of Epilepsies and Epileptic Syndromes (1989) (see Section 17.2) and consistent with partial onset seizures according to the Classification of Epileptic Seizures (1981) (see Section 17.1). If the EEG and brain CT scan and brain MRI were not performed prior to the Screening Visit (Visit 1), the assessment needs to be completed and results must be available prior to Visit 3.
3. Subject must be male or female from 1 month to <4 years of age. Pre-term infants aged <1 year are to be stratified into an appropriate age category using the best estimate of their corrected gestational age.
4. For subjects on adjunctive therapy, subject must be on a stable AED regimen (ie, a maximum of 2 AEDs) for the Selection and Evaluation Periods of the study. Minor adjustments to the

dose of current AEDs are allowed only prior to Visit 1. Monotherapy subjects must not receive AED treatment, receive temporary AED treatment, or switch an AED prior to Visit 1.

5. Subject weighs $\geq 3.0\text{kg}$.
6. Subject may have Vagal Nerve Stimulation (VNS) which has been implanted for at least 6 months prior to Visit 1; the settings must be stable for at least 2 months prior to Visit 1. Activated VNS must be counted as 1 of the 2 AEDs.

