7.2 Treatments to be administered

Each subject will be weighed in kg and will receive 2 equal oral doses of LEV dry syrup 50% dissolved in water; 1 in the morning and 1 in the evening. The weight obtained at every visit will be used to calculate the dose of study medication (mg per kg) for the entire study.

If the subject cannot take LEV dry syrup under a fasting state during the First Period, LEV 100mg/mL concentrate for solution for infusion (clear, colorless, sterile solution) can be used for a maximum of 4.5 consecutive days at each dose at the Investigator's discretion. Levetiracetam injection is infused intravenously over 15 minutes per dose.

The weight and amount of individual dose will be recorded in the CRF and in the drug accountability log for the site. Medication will be allocated by the IVRS.

First Period

Once the subject has fulfilled the eligibility criteria, the subject will enter the Evaluation Period.

Study medication should be given as 2 equally divided doses administered twice daily. The first intake of newly dispensed study medication should occur at Visit 3. Subjects should take IMP according to instructions provided by the Investigator.

[figure not shown]
Subjects aged 1 month to < 6 months will be started on LEV 14mg/kg/day at Visit 3 (Week 0). The dose may be increased by LEV 14mg/kg/day for subjects aged 1 month to < 6 months at 2-week intervals to a maximum dose of LEV 42mg/kg/day. Subjects aged 6 months to < 4 years will be started on LEV 20mg/kg/day at Visit 3 (Week 0). The dose may be increased by LEV 20mg/kg/day at 2-week intervals to a maximum dose of 60mg/kg/day.

At the end of the Evaluation Period, subjects will enter into the Second Period. Subjects who do not enter the Second Period will enter the Down-Titration Period, followed by the Safety Follow-Up Period.

The Down-Titration Period (up to 4 weeks) will consist of the following:

- The dose will be decreased by 14mg/kg/day for subjects aged 1 month to <6 months or by 20mg/kg/day for subjects aged 6 months to <4 years at 2-week intervals to 0mg/kg/day.

Figure 7-1: Schematic for Down-Titration and Safety Follow-Up Periods

*: Safety Follow-Up (SFU) is 2 weeks after final dose of study drug.

EDV=Early Discontinuation Visit; SFU=Safety Follow-Up; V=Visit

Note: The value in parentheses for dose is for subjects 1 month to <6 months of age.

The down-titration procedure needs to be applied in case of early discontinuation.

Second Period

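### Adjacent sentences in Protocol 5.1.2 give different age ranges and conditions for rapid titration, and nothing else in the documents says which governs

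*Protocol*

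**What the plan says.** The ordinary First Period schedule appears in Protocol Sections 1, 5.1.2 and 7.2. For subjects aged 6 months to <4 years, 7.2 reads: "The dose may be increased by LEV 20mg/kg/day at 2-week intervals to a maximum dose of 60mg/kg/day". Younger infants have a parallel rule with 14 mg/kg/day steps.

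Only Section 5.1.2 contains an exception, in two consecutive sentences:

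- The first sentence defines a group, "For the subjects aged 1 month to <12 months who have cluster seizures several times a day", who are also inpatients under a physician's supervision. For them, "the dose can be increased without waiting for the 2-week interval".
- The second sentence opens with a different condition, "If the subject is hospitalized and under supervision of a physician", and continues that "the following rapid titration procedure (dose and interval) will be performed as the most rapid case". It then gives 14 mg/kg/day steps for ages 1 to <6 months and "LEV 20mg/kg/day for subjects aged 6 months to <4 years at 1-day intervals".

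The trial's age range is set in Section 6.1: "Subject must be male or female from 1 month to <4 years of age". SAP 2.3 gives no dosing scheme of its own and refers the reader to Protocol 5.1.2.

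**The concern.** Who may have daily dose increases depends on which of the two sentences a site follows. The first restricts by age and seizure pattern as well as setting. The second restricts by setting alone and names age bands that together span the whole trial population. The wording also moves from permission in the first sentence to a procedure that will be performed in the second.

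At stake is how fast a child aged 12 months to <4 years may be taken to the top dose, which is a safety matter. The titration rule is also part of what the study is meant to support: Protocol 5.4 records the regulator's suggestion that dosage and administration, including how the dose is raised, be established in a confirmatory study.

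**Working it through.** The plan states no figure on this point, so there is none to reproduce. The check sets the passages side by side, followed by simple arithmetic on the size of the gap.

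**The two sentences of Protocol 5.1.2**

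| Element | First sentence | Second sentence |
|---|---|---|
| Age | 1 month to <12 months | 1 to <6 months, and 6 months to <4 years |
| Seizure condition | Cluster seizures several times a day | None stated |
| Setting | Supervised inpatient | Hospitalized and supervised |
| Force | Dose can be increased | Procedure will be performed, as the fastest case |
| Interval | 2-week wait waived, no interval given | 1 day |

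Only the setting agrees. The age range and the seizure condition do not.

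**Search for a passage that decides between them**

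- Sections 1 and 7.2 give the 2-week schedule for the First Period and do not mention rapid titration. They neither confirm the narrower age range nor support the wider one.
- Section 5.4 describes 2-week increases over the 6-week Evaluation Period, also without mentioning the exception.
- Section 5.1.3 concerns the Second Period.
- SAP 2.3 points back to 5.1.2.
- The Amendment 3 entry for 5.1.2 (Section 17.6) shows an ellipsis where this paragraph stands, so it gives no help on intent.

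**Ages on which the sentences disagree**

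- Eligible range: 1 month to <4 years, or 48 − 1 = 47 months of age.
- Outside the first sentence but inside the second: 12 months to <4 years, or 48 − 12 = 36 months of age.
- Two of the four age groups in Section 5.1.5 (1 to <2 years and 2 to <4 years) lie wholly in that range.

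**Time from starting dose to maximum in that range**

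- Number of steps: (60 − 20) / 20 = 2.
- At 1-day intervals: 2 × 1 = 2 days.
- At 2-week intervals: 2 × 2 = 4 weeks.

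**How many enrolled children are of that age**

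Section 5.1.5 plans 38 evaluable subjects "with a minimum of 5 subjects in each age group". If that minimum is met within the 38 (an assumption), the two older groups together hold at least 2 × 5 = 10 subjects and at most 38 − 2 × 5 = 28. This counts children of the relevant age, not children who would be rapidly titrated. The second sentence also requires hospitalization and supervision, and the documents give no count of subjects aged 12 months to <4 years who would meet that.

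**The case against.** The best answer is that the second sentence simply specifies the first. The first sentence waives the wait for supervised inpatients. The second returns to the same setting and caps how fast the waiver may run. Read alone it has little purpose, because nothing would yet have been waived. The 6-months-to-<4-years band is the protocol's standard label for the 20 mg/kg/day increment and may only pair that increment with its usual band. This reading is plausible and may be what was intended. But the text does not say it, and an upper band meant for this group would be expected to stop at <12 months. The objection lowers the probability of misapplication without removing the conflict.

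Three further objections stand, and each limits what a reader might infer:

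- **That Sections 1 and 7.2 contradict 5.1.2.** They state the general schedule in permissive terms and leave out the special case. That is an omission, not a rival age limit.
- **That Visits 4 and 5 otherwise reflect fixed 2-week dose steps, which rapid titration would disturb.** The steps are not fixed. Under 5.1.2 the dose rises only if seizure freedom has not been reached, may be held for a safety concern, and may be lowered once. Rapid titration below 12 months is allowed on either reading, so titration speed can already differ between subjects. The primary variable counts seizures after Visit 5 through Visit 6 (SAP 8.1.1), by which time the third dose level is reachable on the ordinary schedule.
- **That the efficacy listings need a rapid-titration flag.** Protocol 7.2 has individual doses recorded in the CRF, and SAP 10.1 provides listings of study medication administration and exposure. A flag would be a preference and would not cure the wording.

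**Conclusion.** The inconsistency is real: two adjacent sentences of an operative dosing rule differ in age range and in conditions, and no other passage decides between them. On one reading, daily steps stop at 12 months of age and require cluster seizures. On the other, they extend to hospitalized, supervised children up to <4 years.

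The size is a span of 36 of 47 eligible months of age, with a time to maximum dose of 2 days against 4 weeks. A reader might infer that sites are authorized to use daily steps in two whole age groups, or that 10 to 28 children would be exposed. The documents support neither inference. The wider reading is possible, not certain, and the counts bound age eligibility only.

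Actual exposure is unknown and could be zero. Two other rules may narrow it further: recent status epilepticus requiring hospitalization is generally excluded (Section 6.2), and seizure clustering not previously known for the subject leads to withdrawal (Section 6.3).

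Sample size, alpha and power are not affected. The point is one of drafting with a possible safety consequence, and it should be corrected.

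**What to change.** Reconcile the two sentences of Protocol 5.1.2 so that a single age range and a single set of conditions apply to rapid titration, and make clear whether the second sentence only specifies the first. Add a cross-reference to that rule from Sections 1 and 7.2, where the 2-week schedule now appears without the exception. The sponsor and its clinical advisers must decide the age range, conditions and interval.

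The cost is a protocol clarification with its usual approvals. No new data, analysis or change in sample size is needed.
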